8.2 Criteria for stopping procedures in an individual

A subject may be removed from study under the following conditions:

- If a subject satisfies eligibility criteria at screening but in the interval between consent and scanning events happen and the eligibility criteria are no more met.
- If the subject is unable to stay still in the PET scanner for the required study duration.

8.3 Criteria for individual subject withdrawal

A subject may ask to be removed from the study at any time.

A subject may be withdrawn from the study at the discretion of the principal investigator (PI).

9 Outcome Measures

9.1 Primary outcome measure

- Influx constant (Ki) for 18F-FDOPA PET.
- Binding potential relative to non-displaceable binding (BP_{ND}) values for 11C-DASB PET.

9.2 Secondary outcome measures

- Correlation of 18F-FDOPA with co-morbidities (e.g. Co-infections, atherosclerotic cardiovascular disease (ASCVD) risk scores, prior and current drug abuse).
- Correlation of 11C-DASB with Neuropsychiatric evaluation (e.g. depressive and executive function/cognitive scores).
- Correlation of 18F-FDOPA and 11C-DASB with HIV infection parameters (e.g. time since HIV diagnosis, duration of infection before treatment initiation, nadir CD4).

10 Statistical Analysis

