2.2 Secondary Objectives

- To distinguish dopaminergic neurotransmitter damage related to HIV versus co-morbidities.
- To correlate 11C-DASB binding in the brain with depressive symptomatology in optimally-treated HIV-positive subjects.
- To correlate in vivo uptake of 18F-FDOPA and 11C-DASB PET with duration of infection with HIV, the duration of HIV infection prior to the initiation of antiretroviral therapy (ART), and nadir CD4.

3 Subjects

3.1 Description of study population: All Subjects (Groups A-E):

Subjects will include chronically infected HIV-positive subjects with plasma HIV-RNA <100 copies/mm³ or below level of detection (BLD) for greater than one year () along with HIV-negative subjects with and without co-morbidities.

Accrual Ceiling: 155

Dopaminergic arm: 35 HIV-positive and 60 HIV-negative subjects (total 95 subjects)

Serotonergic arm: 30 HIV-positive and 30 HIV-negative subjects (total 60 subjects)

Our target sample size is:

Dopaminergic arm: 25 HIV-positive and 50 HIV-negative subjects (total 75 subjects)

Serotonergic arm: 20 HIV-positive and 20 HIV-negative subjects (total 40 subjects)

Any withdrawals/dropouts will be replaced.

NIH employees may participate if eligible. Subordinates of investigators will not be allowed to participate.

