3.2 Inclusion criteria

Subject groups:

Dopaminergic arm:

Group A: HIV-positive subjects with or without co- morbidities

Group B: HIV-negative subjects with co-morbidities

Group C: HIV-negative subjects without co-morbidities

Serotonergic arm:

Group D: HIV-positive subjects with or without co-morbidities

Group E: HIV-negative subjects with or without co-morbidities

3.2.1 All Subjects (Groups A-E):

1. Men and women, 18-70 years of age
2. Ability to sign informed consent by the subject
3. Subjects may be enrolled in or have been discharged from IRB approved NIH protocols OR subjects may be referred from outside providers/institutions.
4. Has the ability to be seen by an outside medical doctor who provides care.

3.2.2 All HIV-positive Subjects with or without co-morbidities (Groups A [dopaminergic arm, n=25] and Group D [serotonergic arm, n=20])

1. Known and documented HIV-1 infection
2. Plasma HIV-RNA BLD (<100 copies/mm³) for greater than one year since the last available documented viral load measurement.
3. At least one year of continuous ART prior to last documented suppressed viral load measurement and no history of ART modification or interruption since then.

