10.1 Statistical considerations for the FDOPA study

Sample size for the FDOPA PET: There has been no previous imaging of FDOPA in HIV-positive subjects. Based on a paper⁶² evaluating subjects with familial parkinsonism that were either symptomatic or asymptomatic, in comparison to healthy volunteers and subjects with Parkinson's Disease, Ki mean values and standard deviations were reported as shown in **Table 1** below:

Table 1 Ki mean values and standard deviations in subjects with familial Parkinsonism compared to healthy volunteers

		caudate	putamen
Healthy controls	Avg	0.0113	0.01
	SD	0.0017	0.0013
PD	Avg	0.0073	0.0039

	SD	0.0028	0.0013
Familial asymptomatic	Avg	0.008833	0.0067
	SD	0.001358	0.000755
Familial symptomatic	Avg	0.0056	0.00414
	SD	0.001765	0.001324

We believe the HIV-positive subjects will have similar results as the familial asymptomatic PD; while our subjects do not have PD symptoms, they are expected to have defective dopaminergic systems based on the FDG-PET findings. Hence we decided to use the asymptomatic PD data as reflective of the HIV-positive subject group. Since we found the caudate nucleus to be more affected in our subject population than the putamen, the means and standard deviations of Ki values in the HC and asymptomatic familial group were used to calculate the sample size needed for our study. For the second group (HIV-negative subjects), we assumed Ki values to be at a mid-point between HC (mean 0.0113, SD 0.0017) and HIV-positive subjects (familial asymptomatic mean 0.008833, SD 0.001358), with the mid-point value being 0.0100665 (pooled SD 0.001539).

Sample size estimates were for a one-way analysis of variance (ANOVA) comparing the three groups while considering post-hoc pairwise comparisons, particularly between the HIV-positive subjects and the HIV-negative subjects with co-morbidities. Thus, we utilized a more cautious approach focused on being able to detect a difference between these two subject groups using the Ki estimates described above. Calculations yielded a sample size of 23 subjects per group, with alpha=0.05 and 80% power. Considering a 5-10% drop-out rate resulted in a final sample size of 25 per group. Given the ANOVA comparison among three groups, an additional 25 HC would be needed for this study, for a total of 75 subjects equally balanced among the three groups. Subgroup analysis by sex, age, and ethnicity will be carried out during data analysis.

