11.2 Justification for exclusion of children

Subjects younger than 18 years of age are excluded because of radiation risks to children/young adults and because the developing brain is not within the scope of this study.

11.3 Justification for exclusion of subjects over 70 years:

We are excluding subjects over 70 years of age because we want to avoid the potential influence of advanced age on the PET scans.

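### Objective 2.2 asks about duration of infection, but 9.2 measures time since diagnosis, leaves infection onset undated, and correlates it with the scans without allowing for age

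*Combined protocol and SAP*

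**What the plan says.** Section 2.2 sets the third secondary objective as correlating uptake of both tracers with "duration of infection with HIV, the duration of HIV infection prior to the initiation of antiretroviral therapy (ART), and nadir CD4".

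Section 9.2 gives the matching outcome as a correlation with HIV infection parameters, introduced as examples: "time since HIV diagnosis, duration of infection before treatment initiation, nadir CD4".

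The first variable therefore changes between the two sections. The second keeps nearly the same words, and nadir CD4 is unchanged.

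On dating infection, 3.2.2 requires only "Known and documented HIV-1 infection". The schedule of activities (4.3) lists a general medical history and laboratory tests. It does not list a seroconversion date, a last negative test or an estimation rule. Section 10 describes no analysis for these correlations.

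On age, subjects are 18 to 70 (3.2.1). Section 11.3 explains the upper limit: "we want to avoid the potential influence of advanced age on the PET scans". Sections 10.1 and 10.2 plan subgroup analysis by sex, age and ethnicity.

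**The concern.** There are two separate problems.

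**Onset.** Chronic HIV infection can precede its diagnosis by years. Time since diagnosis leaves that interval out. For the untreated period, 9.2 keeps the label but supplies no start date, and diagnosis is the only onset marker the plan names. Were it used, a subject diagnosed late and treated promptly would have a long untreated exposure and a short recorded one. A weak or null correlation could then reflect how exposure was dated and say little about biology.

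**Age.** Time since diagnosis is likely to be longer in older subjects, and the plan itself allows that age may affect the scans. Section 9.2 names a correlation and no covariate. A negative correlation between Ki and time since diagnosis could then be ageing read as an effect of infection.

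At stake is the interpretation of one secondary objective, with 25 HIV-positive subjects for FDOPA and 20 for DASB (3.1).

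**Working it through.** The plan gives no expected correlation, power or test for this objective, so there is no stated figure to reproduce. From the documents come n=25 and n=20 (3.1). The 0.05 level is stated in Section 10 for the group comparisons only, and a two-sided 0.05 test is assumed here. All delays and correlations below are assumptions.

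**1. Untreated duration, if dated from diagnosis.** Let D be infection to diagnosis, T diagnosis to ART, and U = D + T the true untreated duration. The recorded value is T. With k = SD(D)/SD(T) and ρ = corr(D,T):

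corr(T,U) = (1 + ρk) / √(1 + k² + 2ρk)

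| k | ρ = 0 | ρ = -0.5 | ρ = -0.7 |
|---|---|---|---|
| 0.5 | 0.89 | 0.87 | 0.88 |
| 1 | 0.71 | 0.50 | 0.39 |
| 2 | 0.45 | 0.00 | -0.27 |
| 3 | 0.32 | -0.19 | -0.46 |

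Example: k=3, ρ=-0.5 gives (1 - 1.5)/√(1 + 9 - 3) = -0.5/2.65 = -0.19.

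The sign turns negative only when ρ < -1/k. As ρ cannot be below -1, this needs k > 1 as well as an inverse link. With ρ = 0 the correlation shrinks and never reverses.

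The result depends heavily on the inputs. Take T as exponential with mean 3 years, multiplied by exp(-D/4), so that later diagnosis means faster ART. Mean diagnostic delays of 1, 2, 3, 4 and 6 years then give 0.92, 0.65, 0.34, about 0.1 and -0.13. Halving the dependence to exp(-D/8) gives 0.26 at 4 years and -0.01 at 6.

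In years, take exponential times with mean D of 5 and mean T of 2. If they are independent, the quarter of subjects with the longest delay have a true untreated time of about 14 years against 4.7 in the others. They are recorded as 2.0 against 2.0. With a correlation of -0.5 (set on the normal scale), the true times are 12.9 against 5.0 and the recorded times 1.0 against 2.3.

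**2. Effect on power.** If Ki depends linearly on U, the observed r is the true r times the factor in the table. Fisher z, two-sided 0.05, assumed true |r| = 0.50:

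| Case | observed r | power, n=25 | power, n=20 |
|---|---|---|---|
| Onset known | 0.50 | 73% | 62% |
| k=0.5, ρ=0 | 0.45 | 62% | 51% |
| k=1, ρ=0 | 0.35 | 41% | 33% |
| k=1, ρ=-0.5 | 0.25 | 22% | 18% |
| k=2, ρ=-0.5 | 0.00 | 5% | 5% |

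**3. Total duration.** The recorded value is T plus time on ART; the truth adds D. With 1 to 20 years on ART assumed, five scenarios gave correlations of 0.71 to 0.91. Widening to mean delays of 1 to 6 years and up to 25 years on ART gave about 0.64 to 0.99. All were positive.

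**4. Age.** Suppose duration has no effect, and age correlates a with time since diagnosis and b with Ki. The expected simple correlation is then ab. Rejection probability at n=25 by Fisher z uses atanh(|ab|) × √22. For a=0.5, b=-0.4: |ab| = 0.20, 0.2027 × 4.690 = 0.951, and 1 - Φ(1.960 - 0.951) + Φ(-1.960 - 0.951) = 0.156 + 0.002 = 0.158.

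| a | b | ab | rejection at nominal 5% |
|---|---|---|---|
| 0.3 | -0.2 | -0.06 | 6% |
| 0.4 | -0.2 | -0.08 | 7% |
| 0.5 | -0.2 | -0.10 | 8% |
| 0.3 | -0.4 | -0.12 | 9% |
| 0.5 | -0.4 | -0.20 | 16% |
| 0.6 | -0.4 | -0.24 | 21% |

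Simulation with 40,000 runs per row agrees. The numerator of the partial correlation given age is r - ab, which is zero in expectation here, and the simulated partial test rejected about 5% of the time in every row.

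**The case against.** The strongest reply is that little here is documented and much is assumed.

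- **The untreated-duration item was not replaced.** A reader might infer that 9.2 turned both durations into time since diagnosis, so that late-diagnosed subjects are scored as least exposed and the correlation reverses. The documents do not support that. Section 9.2 still names infection before treatment and nowhere says diagnosis is its start. Medical history is taken (4.3) and existing records are reviewed (4.2, 4.4.1), and these may hold earlier negative tests. This stands: the fault is an undefined start date, not a demonstrated mis-scoring. Even with diagnosis as onset, late-diagnosed subjects score lowest only if they also start ART sooner.
- **The documented substitution is mild.** This also stands. Time since diagnosis remains a fair proxy for total duration under most of the assumptions tried.
- **The list in 9.2 is one of examples, and nadir CD4 sits in both sections.** True. Nadir CD4 does not depend on a diagnosis date, so the objective keeps one measure free of the problem.
- **Section 11.3 speaks of advanced age, as a reason to exclude those over 70, and age subgroups are planned.** The first part is fair: the plan does not assert an age effect within 18 to 70, and under weak assumptions the inflation is only 6% to 9%. The second part does not answer the point. Splitting 20 to 25 subjects by age does not adjust these correlations.
- **It is a secondary objective with no power claim.** True, and it limits the weight of the point.

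**Conclusion.** The point holds in limited form. Sections 2.2 and 9.2 name different variables for duration of infection, and onset is undefined for the untreated period. If diagnosis is used, the correlation with true untreated duration is weakened, for example to 0.71 when delay and time to ART vary equally and independently. Loss or reversal needs diagnostic delay to vary more than time to ART together with an inverse link near or beyond -1/k. The documents give no delays, so this is a possibility and not a finding. For total duration the proxy is attenuated (about 0.64 to 0.99 in the scenarios run) and not reversed.

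The age problem is independent of how onset is dated. At n=25, with no true duration effect, the nominal 5% test rejects about 6% to 21% of the time over the assumed age correlations, and conditioning on age restores about 5%. The same reasoning applies to BP_ND at n=20.

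The primary group comparisons are not touched.

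**What to change.** 1. In 9.2, report the correlations of Ki and BP_ND with the HIV infection parameters as partial correlations given age. Age is already collected. The cost is one degree of freedom. Where age and duration are closely related, less independent variation in duration is also left: at a correlation of 0.6, 1 - 0.36 = 64% of its variance.
2. In 2.2 and 9.2, call the measures *time since diagnosis* and *diagnosis-to-ART interval* wherever onset is not bounded by an earlier negative test, and limit the conclusions to those measures. The cost is wording and a narrower claim.

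If earlier negative test dates are found in the records, a sensitivity analysis in subjects with bounded onset is a useful option, though the subset would be smaller. Ranking nadir CD4 first is a matter of preference and is not needed. No added visit, scan or subject is required.

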10.1 Statistical considerations for the FDOPA study

Sample size for the FDOPA PET: There has been no previous imaging of FDOPA in HIV-positive subjects. Based on a paper⁶² evaluating subjects with familial parkinsonism that were either symptomatic or asymptomatic, in comparison to healthy volunteers and subjects with Parkinson's Disease, Ki mean values and standard deviations were reported as shown in **Table 1** below:

Table 1 Ki mean values and standard deviations in subjects with familial Parkinsonism compared to healthy volunteers

		caudate	putamen
Healthy controls	Avg	0.0113	0.01
	SD	0.0017	0.0013
PD	Avg	0.0073	0.0039

	SD	0.0028	0.0013
Familial asymptomatic	Avg	0.008833	0.0067
	SD	0.001358	0.000755
Familial symptomatic	Avg	0.0056	0.00414
	SD	0.001765	0.001324

We believe the HIV-positive subjects will have similar results as the familial asymptomatic PD; while our subjects do not have PD symptoms, they are expected to have defective dopaminergic systems based on the FDG-PET findings. Hence we decided to use the asymptomatic PD data as reflective of the HIV-positive subject group. Since we found the caudate nucleus to be more affected in our subject population than the putamen, the means and standard deviations of Ki values in the HC and asymptomatic familial group were used to calculate the sample size needed for our study. For the second group (HIV-negative subjects), we assumed Ki values to be at a mid-point between HC (mean 0.0113, SD 0.0017) and HIV-positive subjects (familial asymptomatic mean 0.008833, SD 0.001358), with the mid-point value being 0.0100665 (pooled SD 0.001539).

Sample size estimates were for a one-way analysis of variance (ANOVA) comparing the three groups while considering post-hoc pairwise comparisons, particularly between the HIV-positive subjects and the HIV-negative subjects with co-morbidities. Thus, we utilized a more cautious approach focused on being able to detect a difference between these two subject groups using the Ki estimates described above. Calculations yielded a sample size of 23 subjects per group, with alpha=0.05 and 80% power. Considering a 5-10% drop-out rate resulted in a final sample size of 25 per group. Given the ANOVA comparison among three groups, an additional 25 HC would be needed for this study, for a total of 75 subjects equally balanced among the three groups. Subgroup analysis by sex, age, and ethnicity will be carried out during data analysis.

10.2 Statistical Considerations for the DASB Study

In our previous study we were able to show higher ¹¹C-DASB uptake in depressed subjects compared to non-depressed subjects using a sample size of 9 each. From our recent animal data, the mean BP_{ND} before inoculation was 2.11 (0.51), while the mean values at the last time point was 2.69 (0.56). We expect the difference between pre- and post- inoculation monkeys (average SD of 0.53, differences in means of 0.56) to be the same in the two independent groups (HIV-positive vs HIV-negative, HC).

Table 2. Numeric Results for Two-Sample T-Test Allowing Unequal Variance

Alternative Hypothesis: H1: $\delta = \mu_1 - \mu_2 \neq 0$

Target Power	Actual Power	N1	N2	N	μ_1	μ_2	δ	σ_1	σ_2	Alpha
0.80	0.81642	15	15	30	2.1	2.7	-0.6	0.5	0.6	0.050

Protocol Number: 18CC0117

Version Date: 04/26/2022

0.81	0.81642	15	15	30	2.1	2.7	-0.6	0.5	0.6	0.050
0.82	0.84202	16	16	32	2.1	2.7	-0.6	0.5	0.6	0.050
0.83	0.84202	16	16	32	2.1	2.7	-0.6	0.5	0.6	0.050
0.84	0.84202	16	16	32	2.1	2.7	-0.6	0.5	0.6	0.050
0.85	0.86442	17	17	34	2.1	2.7	-0.6	0.5	0.6	0.050
0.86	0.86442	17	17	34	2.1	2.7	-0.6	0.5	0.6	0.050
0.87	0.88395	18	18	36	2.1	2.7	-0.6	0.5	0.6	0.050
0.88	0.88395	18	18	36	2.1	2.7	-0.6	0.5	0.6	0.050
0.89	0.90091	19	19	38	2.1	2.7	-0.6	0.5	0.6	0.050
0.90	0.90091	19	19	38	2.1	2.7	-0.6	0.5	0.6	0.050

Based on that assumption, 19 subjects are needed per group, at alpha = 0.05 and power at 90%, with 5% dropout rate resulting in N= 20 per group.

However, since monkey data might not accurately reflect human data, we are planning on reassessing our results after ten people in each group are recruited in order to re-estimate the accuracy of presumed variance and if deemed necessary increase the sample size accordingly. This would guarantee that the sample size calculation is based on the estimate of variance. We will not have an interim analysis. As part of the final data analysis, subgroup analysis by sex, age, and ethnicity will be carried out.

The total accrual ceiling for this protocol including 18F-DOPA and 11C-DASB studies is 155 subjects.

10.2.1 Data analysis:

18F-DOPA: PET scans will be reconstructed in 22 frame protocol (3×20, 2×30, 2×60, 3×120, 8×300 and 4×600 s) using the ordered-subsets expectation maximum (OSEM) algorithm, in a 31× 31-cm field of view and a 256×256 pixel matrix with a pixel size of 1.2×1.2 mm. PET frames will be corrected for radioactive decay.

The attenuated and decay corrected scan will be registered to the same subject's anatomical magnetic resonance imaging (MRI) scan (obtained under our protocol or other NIH approved protocols if applicable). The MRI scans will then get affine normalized to a brain MRI template and volumes of interest will be drawn on the template. The kinetic rate constant Ki for 18F-DOPA uptake will then be calculated using a linear fit based on the Patlak method ⁶³ for the VOIs with a time activity curve in the occipital reference region as the input function. Ki values will then be compared across subject groups.

11C-DASB: dynamic PET imaging will be obtained in list mode for a total scan duration of 90 min. PET scans will be reconstructed in 22 frame protocol (3×20, 2×30, 2×60, 3×120, 8×300 and 4×600 s) using the OSEM algorithm, in a 31× 31-cm field of view and a 256×256 pixel matrix with a pixel size of 1.2×1.2 mm. PET frames will be corrected for radioactive decay.

The attenuated and decay corrected scan will be registered to the same subject's anatomical MRI scan (obtained under our protocol or other NIH approved protocols if applicable). The MRI scans will then get affine normalized to a brain MRI template (MNI) and volumes of interest will be drawn on the template. The binding potential values of 11C-DASB in various parts of the brain will then be calculated using 2-

parameter multilinear reference tissue parametric imaging method (MRTM2) using the cerebellum as a reference region.

10.2.2 Interpretation of 18F-FDOPA and 11C-DASB PET Imaging

Data analysis and interpretation will be done in a blinded manner. When the data is transferred from the PET server to the investigator's server, one operator (co-investigator) will make sure the images are de-identified and saved prior to detailed analysis. The same operator will eventually re-identify the data once the analysis is complete.

11 Human Subjects Protection

11.1 Subject selection

Subject selection will be equitable among eligible patients. No population will be excluded from the study on the basis of race, ethnicity, sex, disability, nationality or religion.

11.2 Justification for exclusion of children

Subjects younger than 18 years of age are excluded because of radiation risks to children/young adults and because the developing brain is not within the scope of this study.

11.3 Justification for exclusion of subjects over 70 years:

We are excluding subjects over 70 years of age because we want to avoid the potential influence of advanced age on the PET scans.

11.4 Justification for exclusion of non-English speakers

Non-English-speaking participants are not eligible for enrollment in our protocol because many of the neuropsychological subtests that are necessary to our study are only validated in English.

11.5 Justification for inclusion or exclusion of other vulnerable subjects

Exclusion of Pregnant or Lactating Women:

Women who are pregnant or lactating are not eligible to enter the study. The study requires exposure to radiation, which could pose a risk to the fetus. Lactating females are excluded due to exposure to the radioactive compound for PET scans, which may be excreted in the breast milk and could be potentially harmful to breast-fed infants.

11.6 Justification for Inclusion of Neurocognitively Impaired Subjects

By definition, subjects with HAND are neurocognitively impaired. Because of the need to study this disorder, we must include subjects with neurocognitive impairment into this study. However, each such subject must have capacity to provide informed consent to participate. If subjects, at any point during the screening and study procedures, become decisionally impaired and lose their capacity to provide informed consent, they will be excluded.

